### *Questionnaire Scheduling and Timing*

Research staff will begin attempting to contact participants (patient and caregiver) for scheduling purposes one month prior to the ideal administration date for the 3-, 6- and 9-month post-discharge questionnaires. Research staff will attempt to complete the questionnaire no more than 15 days before or 30 days after the ideal administration date for the 3-, 6-, and 9-month post-discharge questionnaires, with the exception of the two-week extension rule listed below). Research staff should attempt to complete each questionnaire as close to the ideal administration date as possible (e.g. 3 months following discharge for the 3-month post-discharge questionnaire).

Research staff will begin attempting to contact participants (patient and caregiver) for scheduling purposes two months prior to the ideal administration date for the 12-month post-discharge and one year following injury questionnaires. Research staff will attempt to complete these questionnaires no more than two months before or after the ideal administration date for the 12-month questionnaire and Form II (see two-week extension rule below). In addition, a minimum of 30 days must pass between the 9- and 12-month questionnaires.

Patient participants that started or completed the post-discharge questionnaires prior to the window start date should be contacted by research staff during the window to review the completed items to make sure nothing has changed. The date of the call back occurring within the follow-up window should be used as the questionnaire date. If a call back cannot be completed, the original questionnaire date outside the follow-up window should be used.

**Two-Week Extension Rule:** Post-discharge questionnaires that have been started but cannot be completed by the time the data collection window closes can be completed within two weeks after the window closes. The questionnaire date should be the date the questionnaire was started.

**Four-Week Completion Rule:** Post-discharge questionnaires that have been started but not completed during the first contact should be completed within 4 weeks. The questionnaire date should be the date of initial data collection. If it takes longer than 4 weeks to complete the questionnaire, data collected during the initial data collection period should be verified, and the questionnaire date should be the second date that data was collected. In the unusual case where the 2 week extension window is used to complete the questionnaire beyond the 4 week time frame, (e.g. questionnaire started January 1st, questionnaire window closes January 30th, questionnaire completed February 5th), the questionnaire date should be the date of data collection that was in the questionnaire window (January 1st in this example).

**Mailout Option:** The mailing of the questionnaire will trigger the 2 week extension to the questionnaire window. Example: if research staff mail the questionnaire July 18, 2018, and the end of the window is August 31st, research staff can then receive/collect data through September 14th.

Mailouts are exempt from the four-week extension rule listed above.

**Patient Participants Only (i.e. Not Caregiver Participants):** If adequate data are not obtained from the participant by telephone or by mailout two weeks before the end of the window, the mailout questionnaire should be sent a significant other SUBID and mailing date have been added to the form, along with a self-addressed return envelope. Like the mailing of the questionnaire to the patient participant, the mailing will trigger the 2 week extension to the questionnaire window. Example if research staff mail the questionnaire July 18, 2018, and the

end of the window is August 31st, research staff can then receive/collect data through September 14th.

Missing data may not be filled in using data obtained outside the questionnaire window and two-week extension rule unless approved by the lead site.

To classify a questionnaire as “followed” an interview or mailout must be started. There is no minimum number of data elements that need to be answered.

Research staff will attempt to reach participants to complete these questionnaires until: 1) the questionnaire is completed, 2) the participant declines or is deemed unable to complete the questionnaire (withdrawal, death, etc.), or 3) the questionnaire window (and two-week extension rule, if applicable) expires.

Research staff may send out a letter in advance to both patient and caregiver participants reminding them of the upcoming questionnaires.

Any administrations that fall outside of the windows described above will be documented as protocol deviations using the study note-to-file form.

All follow-up data described above will be entered in with the participant's ID, i.e. not name into the NDSC centralized database via the 'Data' tab.

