### **Follow Up Data Collection**

#### ***3, 6, 9 and 12 Months Post Hospital Discharge Questionnaires: Patient Participant***

The 3, 6, 9 and 12 months post hospital discharge questionnaire will take approximately 25-30 minutes to complete, and will be completed by phone, in person, or via postal mail (see 'Mailout Option' section below for more detail).

The post-discharge questionnaire will consist of the following measures:

1. **Participation Assessment with Recombined Tools-Objective 17 (PART-O) -** measure of community participation.
2. **Quality of Life after Brain Injury Scale (QoLIBRI)** - The QoLIBRI is a patient-reported instrument specifically created to measure the patient's perception of their health-related quality of life following TBI.
3. **Cornell Services Index**- The Cornell Service Index is a widely used measure of healthcare services utilization, and will include number of hospitalizations and days hospitalized, number of emergency department visits, as well as number and type of clinic visits. We will be providing each participant at baseline a tool that will help participant's collect this information.
4. **Street Address:** We will collect street address for data analysis purposes during each of the discharge questionnaires. We would then send each participant's address to the national database at the National Data and Statistical Center. The National Data and Statistical Center uses the address to get information about the socioeconomic status of each participant based on the communities they reside, contracting with a service that helps with obtaining data from neighborhood databases. Both the National Data and Statistical Center and the contractor are required by law to keep the information confidential.

5. **Insurance Type/Coverage:** We will collect insurance type/coverage for data analysis purposes during the 6- and 12-month discharge questionnaires.
6. **Satisfaction with Care:** We will collect information about how satisfied participants were with their healthcare during the 6- and 12-month discharge questionnaires.

*One Year Following Injury Questionnaire: Patient Participant*

Patient participants not enrolled into TBIMS concurrently will complete a questionnaire about one year following injury ("Form II"). The questionnaire collects demographic and injury related data and clinical history will be collected in interview format. The questionnaire will take about 45-60 minutes to complete.

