#### **Participant Retention (MD-1, MD-4)**

We will use participant retention strategies that we have refined in the TBIMS with specific SOP. We anticipate at least 80% enrollment rate in this study due to the broad eligibility criteria and flexible interventions being offered. In addition, the six TBIMS sites included in the study have a

retention rate of 94% at one-year follow up for TBIMS participants even though there is less contact with the patient across the first year than we will have in the current study, which may increase our ability to retain subjects over time. We will use culturally sensitive, evidence-based practices derived from other successful real-world trauma treatment trials.

Key strategies include: attempting contacts at multiple times of the day and multiple days of the week, including weekends; collecting contact information on three or more people who will know the whereabouts of the patient one year later; obtaining multiple means of contacting each person (home phone, work phone, email), updating contact information frequently; sending birthday/holiday cards, requesting change of address notification from the post office; providing financial incentives for participation; and using fee-based Internet search engines such as TLO. In addition, research staff may send a letter to both patient and caregiver participants indicating that they have been unable to reach them and request the participant contact research staff to arrange for upcoming questionnaires. For any participants who do not complete a follow-up questionnaire, reasons for the lack of follow-up will be recorded (e.g., physically or cognitively unable and proxy not available, not available [e.g., hospitalized, incarcerated], death, withdrawal from study, no response to contact despite repeated attempts, etc.

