### Power for Secondary Outcomes

For Aim 3, we consulted our stakeholders to determine what would represent meaningful differences in healthcare utilization. Based on these discussions, we will categorize completed planned outpatient visits in “less than 50%,” “between 50 and 75%,” and “more than 75%.” Based on highly conservative estimates from data collected on patients who were eligible (based on insurance, geography and preference) and referred to Moss Rehab Hospital (one of our study sites), 4%, 17%, and 79% of the individuals received “less than 50%,” “between 50 and 75%,” and “more than 75%” of their scheduled physical therapy, occupational therapy, and speech therapy care visits (these data do not include other outpatient visits, such as mental health and primary care visits, that are known to have low adherence rates). Under the assumptions that our RDP group would have a proportion of 0.79 of people going to more than 75% of their scheduled visits, with a significance level of 0.05, power of 0.80, and varying the sample size from 500 to 900, we calculated the size of change in the proportion of people receiving 75%+ visits in the RTP group that we would be able to detect. We would be able to statistically detect a proportion of 0.88 in the RTP group with a sample size of 500 and a proportion of 0.86 with 900 (see graph below). Therefore, we would have enough power to detect a small change in proportions.

[figure not shown]
We will also test differences in number of hospitalizations, number of emergency department visits, and number of unplanned outpatient visits per year. These outcomes will be compared using a Poisson model. For the power analysis, we adjusted the significance level to 0.017 after using Bonferroni adjustment (0.05/3), and we considered sample sizes of 700, 800, and 900 (to assess the effect of attrition of roughly 10% and 20%). From our previous work, we only have rough estimates of the events of interest (0.42 hospitalizations per year from [name] et al. and 2.25 medical encounters of any type (not distinguished as planned or unplanned) per year from Salisbury et al.). Therefore, we considered the base rates of 1-5 events per year for the RDP group and calculated the power of detecting a decrease in that rate of 10%, 20%, 30%, and 40% in the RTP group. Using G\*Power and the specifications above, the summary of the findings are as follows:

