**Aim 1, Hypothesis 1:** Both the PART-O-17 and the QoLIBRI measures are numeric with a fairly large range that can be considered as continuous for data analysis. We will test the difference in means for PART-O-17 and QoLIBRI between the two groups at 6-month post-discharge using a two-sided t-test for independent samples. We will also test if the intervention has a long-term effect by comparing the two groups at 12-months post discharge using the same type of t-test.

**Aim 2, Hypothesis 2:** To compare the trajectory of improvement for 3-, 6-, 9- and 12-months post-discharge, we will plot individual trajectories over time and if it appears that the majority of people are leveling off over time we will consider a growth model. Otherwise, we will use a linear mixed model, with the outcome (PART-O-17 or QoLIBRI) as the response variable, and time and other factors (such as age, sex, race/ ethnicity, education, injury severity) as explanatory variables, and add intervention group and its interaction with time to test whether the interventions and time had an effect in the trajectory of the outcome.

**Aim 3, Hypothesis 3:** To compare the healthcare utilization in the first-year post discharge, the two groups will be compared on the distribution of categories of completed planned outpatients visits (less than 50%, between 50 and 75%, and more than 75%) by using a Chi-Square test. Both, the number of urgent care visits and the number of unplanned hospitalizations will be compared by means of a Poisson regression, which will include group and possibly adjusting for other factors (age, sex, race/ethnicity, education, injury severity). A statistically significant coefficient for intervention groups will show that the two groups differ in emergency and unplanned medical visits.

**Aim 4, Hypothesis 4a:** To compare caregiver burden, HRQOL, and satisfaction with roles and activities, we will apply t-tests for difference of means for independent samples for those measures that are found to have a normal distribution. We will also conduct heterogeneity of treatment effects analyses as we planned for other measures.

**Aim 4, Hypothesis 4b:** Using the Bakas Caregiving Outcomes Scale, Zarit Burden Interview, Sf-12, and the PROMIS Satisfaction with Social Roles and Activities for caregivers at 3-, 6-, 9- and 12-month follow-ups as response variables, we will fit a linear mixed model or growth model similar to the ones in hypothesis 2.

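### The Aim 3 Poisson comparison of first-year utilisation counts has no exposure term, although observed time will differ between patients and may differ between arms

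*Combined protocol and SAP*

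**What the plan says.** The Aim 3 paragraph of Data Analysis Plan Specific to Each Aim sets the period: "To compare the healthcare utilization in the first-year post discharge". Urgent care visits and unplanned hospitalisations "will be compared by means of a Poisson regression, which will include group and possibly adjusting for other factors"; the factors it names are age, sex, race/ethnicity, education and injury severity. No offset, person-time or annualisation rule appears there or elsewhere in the document. Power for Secondary Outcomes speaks of "number of hospitalizations, number of emergency department visits, and number of unplanned outpatient visits per year" and takes base rates of 1 to 5 events a year, but does not say how a yearly count is formed when a patient is observed for more or less than a year.

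The counts come from the Cornell Services Index at 3, 6, 9 and 12 months, which "will include number of hospitalizations and days hospitalized, number of emergency department visits, as well as number and type of clinic visits". Neither a recall period nor event dates are described.

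Under Questionnaire Scheduling and Timing, the first three forms are due "no more than 15 days before or 30 days after the ideal administration date for the 3-, 6-, and 9-month post-discharge questionnaires". For the last, "Research staff will attempt to complete these questionnaires no more than two months before or after the ideal administration date for the 12-month questionnaire", with at least 30 days after the 9-month form. A form already started "can be completed within two weeks after the window closes", but it keeps its start date.

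The same section foresees forms not completed because of withdrawal or death, and the Incarceration section suspends questionnaires. Table 1 (Recruitment/Enrollment) plans for 80% retention, that is 180 of 900 patients lost. Patient Unable to Provide Consent withdraws certain proxy-enrolled participants who prove unable to take part: at one month in RTP and at three months in RDP. The missing-data text describes imputation for a continuous variable and does not mention a partly observed count.

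**The concern.** A Poisson regression of a count on group, with no exposure term, estimates the ratio of mean counts. That equals the event-rate ratio multiplied by the ratio of mean observed times. If the arms are observed for different lengths of time on average, the group coefficient mixes the two, and Hypothesis 3's predicted reduction in urgent and unplanned care could be hidden or exaggerated.

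Two features of the design could separate the arms. The arm-specific withdrawal times tend to shorten observation in RTP. RTP also has about 12 scheduled care-manager contacts that RDP lacks, which could affect retention. Leaving the denominator unspecified also leaves its choice open until the data have been seen.

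**Working it through.** **The plan's own power figure.** Inputs from Power for Secondary Outcomes: alpha 0.017 (two-sided assumed), N = 700 to 900, 1:1 allocation, rate ratio 0.80. With exactly one year per patient, expected events are E0 = (N/2) × base rate and E1 = 0.80 × E0, and SE(log ratio) = √(1/E0 + 1/E1). At base rate 2 and N = 900, E0 = 900, E1 = 720 and SE = 0.050. Then |ln 0.80|/SE = 0.2231/0.050 = 4.46, and 4.46 − 2.39 = 2.08, giving power 0.98. At N = 700 and 800 it is 0.94 and 0.97. The stated power of at least 80% for base rates of 2 and above therefore reproduces. At base rate 1 the detectable decrease is 23.0%, 21.6% and 20.4% for N = 700, 800 and 900, against the stated 22 to 25%. These calculations give every patient one full year.

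**Observed time under each reading of recall.** The two readings exclude each other.

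- Since the last interview: coverage for a full completer runs to the last form, so from 12 − 2 = 10 to 12 + 2 = 14 months.
- Fixed 3 months: four forms cover a nominal 12 months for everyone, but unevenly. Forms at months 10 and 11 overlap by 3 − 1 = 2 months. Forms at months 8.5 and 14 leave 14 − 3 − 8.5 = 2.5 months uncovered. Each missed form loses 3 months.

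Neither reading gives every patient the same clean year.

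**Windows alone.** If both arms share the same distribution of observed time T, the ratio of means is 1 and there is no bias. The extra variation is variance/mean = 1 + rate × Var(T)/E(T). Assuming T is uniform on 10 to 14 months, Var(T) = (4/12)²/12 = 0.0093 and E(T) = 1 year. This gives 1.01 at base rate 1 and 1.03 at base rate 3. With 20% also stopping at 3, 6 or 9 months it is 1.06 and 1.19.

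**Unequal loss by arm (assumed; the documents give no split).** If patients lost contribute half a year on average, mean time = retained + 0.5 × lost.

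| Loss RTP / RDP | Mean time RTP / RDP (years) | True 1.00 appears as | True 0.80 appears as |
|---|---|---|---|
| 20% / 20% | 0.900 / 0.900 | 1.00 | 0.80 |
| 17.5% / 22.5% | 0.9125 / 0.8875 | 1.03 | 0.82 |
| 15% / 25% | 0.925 / 0.875 | 1.06 | 0.85 |

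The sign can reverse: a mean of 11 months in RTP against 12 in RDP makes a true 1.00 appear as 11/12 = 0.92.

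**Simulation of the 15% / 25% case.** N = 900, 3,000 runs, constant event rates, completers uniform on 10 to 14 months, losses at 3, 6 or 9 months, nominal alpha 0.017.

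| Base rate | False positives, no offset | False positives, offset | Power at 0.80, no offset | Power at 0.80, offset |
|---|---|---|---|---|
| 1 | 0.067 | 0.016 | 0.44 | 0.72 |
| 2 | 0.114 | 0.019 | 0.77 | 0.97 |
| 3 | 0.174 | 0.017 | 0.92 | 1.00 |

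With the offset, the estimated ratios return to 1.00 and 0.80.

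**The case against.** The strongest reply is that the plan is silent rather than wrong. It speaks of events per year, it has general missing-data rules, and it assigns scoring, missing-data rules and planned analysis procedures to a manual of procedures that is not among these documents. The visit windows are the same in both arms and the assessors are masked. All of this is fair, and it limits the point: nothing says that a missed form is scored as zero, and windows by themselves do not bias the comparison. What remains is that the model's terms are listed, down to optional covariates, without exposure. The phrase per year defines no denominator, and the imputation text is worded for continuous variables.

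A reader might go further in three ways that the documents do not support.

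- That the plan itself expects better retention in RTP. The remark in Participant Retention that contact "which may increase our ability to retain subjects over time" compares this study as a whole with TBIMS follow-up, not RTP with RDP.
- That 80% retention means 80% of person-time. It counts patients, and those lost contribute time before they leave. Treating 85% against 75% as person-time would give 0.85/0.75 = 1.13 in place of about 1.06.
- That the 10 to 14 month span and the gaps and overlaps occur together. Each needs a different recall period. Nor does the two-week extension widen the span for a form already started, since that form keeps its start date.

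**Conclusion.** The concern holds in a limited form. As written, the Aim 3 model compares counts over unequal observed time with nothing to adjust for it. Most of the inequality that the windows create is noise common to both arms. Bias requires a difference between arms in mean observed time. The arm-specific withdrawal times and the additional RTP contacts make that possible, but they may act in opposite directions, and neither the sign nor the size of the net effect can be read from the documents. A claim that the Aim 3 result will be biased, or biased in a known direction, would go too far.

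The figures of 1.06 for a null effect and 0.85 for a true 0.80 are an illustration. They rest on the assumed 15% and 25% losses, mid-year loss on average and constant event rates. With equal observation both distortions vanish. The outcomes are secondary and confidence is moderate, because the recall period and the manual of procedures are not available. The plan should still be changed, since the remedy is cheap and costs nothing if the arms prove balanced.

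**What to change.** In the Aim 3 paragraph of the analysis plan:

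1. Include log(days covered by the completed questionnaires) as an offset in each Poisson model.
2. Make the count and the days refer to the same interval. Use all days covered, including any after day 365, unless event dates exist that allow both to be cut at day 365. Capping only the offset would create a new mismatch, because the forms are described as collecting numbers of events and the last may run to month 14.
3. State the recall period of the Cornell items, since days covered cannot be derived without it. Under a fixed recall period, sum the periods of the completed forms, so that any overlap enters both count and days.
4. End coverage at death or at the last completed questionnaire, and say how missed forms and patients with no completed form are handled. The latter have no covered time, so the offset is undefined for them.

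The cost is a few sentences and one variable derived from discharge and questionnaire dates already recorded. No new data are needed: Appendix 1 has the 12-month forms due by 10/31/2022 and the analyses due on 7/15/2023. The offset does not correct for loss that is itself related to event risk, so reasons for loss and days covered should be reported by arm.

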    - ii. If No: Staff will deem the patient ineligible due to inability to complete study procedures due to cognitive/verbal limitations AND not having a proxy to assist with study procedures.

\*If the proxy individual is not enrolled as a caregiver participant in the study, the TCM would only engage the proxy individual in resource facilitation and the needs assessment as it specifically pertains to the patient participant. The TCM will not conduct a caregiver needs assessment with the proxy or provide resources that pertain specifically to the proxy individual as they are not enrolled as a caregiver. If the TCM infers that the proxy individual would like to participate in the needs assessments/resource facilitation as it pertains to them (e.g., as the caregiver), the TCM would remind the proxy individual in a non-coercive manner of the opportunity to participate as a caregiver participant. This would require the completion of the informed consent process with the proxy individual as per study protocol.

\*\*In this scenario, the proxy individual would not complete the QOLIBRI as part of the post-discharge questionnaire. In addition, the individual would not complete the following items on the Form II: SWLS, GEN, GNHLTH, PHQ, GAD

\*\*\*Staff will withdraw the patient participant following randomization if the participant is deemed unable to participate due to limitations within the following timeframes:

1. The TCM will withdraw the patient participant one month following discharge if randomized to RTP arm of the study;
2. Blinded staff will withdraw the patient participant three months following discharge if randomized to RDP arm of the study;

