#### *Primary Outcomes*

Aims 1 and 2 will address the primary outcomes of 1) Participation in Usual Roles and Activities: Participation Assessment with Recombined Tools-Objective 17 (PART-O) and 2) Health-related Quality of Life: Quality of Life after Brain Injury Scale (QoLIBRI)

Participation Assessment with Recombined Tools – Objective 17 (PART-O-17): Since the resumption of life roles and re-integration into the community drives patient and family decisions regarding rehabilitation care, community participation, as measured by the PART-O-17, was chosen as the primary outcome variable in the current study(**RQ-6, PC-1, PC-3**). The PART-O-17 is a patient-reported (or family member proxy-reported) measure of the International Classification of Functioning (World Health Organization) construct of “participation,” which is defined as involvement in life situations at the societal level as reflected in fulfillment of developmentally and culturally appropriate roles such as worker, student, spouse, parent, or citizen. All major conceptual models of disability (see, for example, Institute of Medicine’s Disablement Model) place considerable emphasis on fulfillment of social roles similar to the manner in which participation is defined in the International Classification of Functioning. The PART-O instrument is based on items derived or modified from three measures most commonly found in the TBI literature: Community Integration Questionnaire; Participation Objective, Participation Subjective; and the Craig Handicap and Assessment Reporting Technique.

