When missing values are present we will check the missing mechanism, and if it allows for imputation, we will do so according to the appropriate methods for a continuous variable, using multiple imputation strategies (most likely using maximum likelihood methods). We will perform sensitivity analysis of the results by performing the data analysis using the most conservative approach of removing the data from individuals with missing outcome values from the analysis, or if it a missing value in a covariate, removing the covariate from the model. The results of the analysis with imputed data and complete data will be compared to assess whether they differ and both results will be reported. The analyses for aims related to longitudinal trajectory rely on statistical methods (mixed generalized linear models) that are robust to missing data at individual time points. In addition, all reasons for drop-out and missing data will be recorded and will be reported in all reports and publications (**MD-2, MD-3, MD-5**).

**Plan for analysis of COVID-19 Pandemic impact:** We propose to add the following steps to the data analysis in order to take the pandemic into account: 1) Analyze the patterns and

causes of refusal to participation in the study before and during the pandemic to determine if the populations in the two periods are coming from the same base population; 2) Analyze the patterns of missing data, comparing them between before and during the pandemic to determine whether we need to additionally add an indicator of the time of data collection (before or during pandemic) as another factor in the generation of the imputed outcome data; 3) analyze the primary and secondary outcomes in an intention-to-treat manner as proposed in the protocol. We will follow with another data analysis that will add in the model time of data collection (pre/post pandemic) and its interaction with intervention type as possible explanatory factors to determine the potential impact of change in timing of enrollment or unaccounted for changes in the intervention.

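### The last-step mailout to a significant other carries the QoLIBRI with no exclusion and no stated record of who answered, so some values of a primary outcome could be proxy ratings

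*Combined protocol and SAP*

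**What the plan says.** All places are in the combined protocol and SAP.

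- **Who reports.** Under the 3, 6, 9 and 12 month patient questionnaires: "The QoLIBRI is a patient-reported instrument specifically created to measure" the patient's perception of health-related quality of life. The Primary Outcomes section treats the other primary measure differently: "The PART-O-17 is a patient-reported (or family member proxy-reported) measure".
- **Proxy rule.** A footnote under Patient Unable to Provide Consent (Recruitment) deals with a patient who cannot consent and has a helper for the questionnaires: "In this scenario, the proxy individual would not complete the QOLIBRI as part of the post-discharge questionnaire".
- **Mode.** The post-discharge questionnaire lists the QoLIBRI as its second measure and "will be completed by phone, in person, or via postal mail".
- **Last-step mailout.** Under Questionnaire Scheduling and Timing, in the paragraph for patient participants only: "If adequate data are not obtained from the participant by telephone or by mailout two weeks before the end of the window", then "the mailout questionnaire should be sent a significant other". There is no condition on capacity and no QoLIBRI exception.
- **Respondent record.** The only stated rule, under Caregiver Participants in Recruitment, concerns which caregiver answers when more than one is enrolled.
- **Analysis.** The Data Analysis Plan compares QoLIBRI means at 6 months by a two-sided t-test. For missing values the mechanism is checked, and "if it allows for imputation, we will do so according to the appropriate methods for a continuous variable". A complete-case analysis is run as well, and both results are reported.

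**The concern.** The protocol withholds the QoLIBRI from proxies in one place. In another it sends a form containing the QoLIBRI to a third party in the patient's stead, without comment. A site following the second instruction literally could return a QoLIBRI filled in by a spouse or parent, and nothing stated afterwards would identify it.

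Two things are at stake. First, a primary outcome defined as the patient's own view would mix two kinds of rater. Second, the mix could differ by arm: RTP adds about 12 scheduled contacts over six months, which may change how often patients can be reached for their own questionnaire. That is plausible, but the documents do not state it. Follow-up counts would not reveal the problem either, because a questionnaire counts as followed once a mailout or interview is started, with no minimum number of answers.

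**Working it through.** **Comparison of the texts.** There is no QoLIBRI figure in the plan to reproduce, since the power sections rest on PART-O-17.

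1. The proxy footnote covers patients unable to consent at enrolment who have a helper. It does not mention the later mailout.
2. The mailout paragraph is triggered by inadequate patient data two weeks before the window closes, whatever the patient's capacity. It does not mention the footnote.
3. The post-discharge questionnaire includes the QoLIBRI and may be done by post. The form that goes out therefore contains it unless someone removes it.
4. Family proxy report is written in for PART-O-17 and not for the QoLIBRI, so the intent for the QoLIBRI is self-report. The mailout paragraph does not carry that intent through.

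**Possible bias if proxy answers were scored.** Suppose proxies differ from patients by a constant g (in SD) and the arms have proxy shares p1 and p2. The observed difference is then the true difference plus (p1 − p2) × g. Neither quantity is in the documents, so both are assumed:

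- Difference in share 0.05, g = 0.3: 0.05 × 0.3 = 0.015 SD.
- Difference in share 0.05, g = 0.5: 0.05 × 0.5 = 0.025 SD.
- Wider range: 0.02 × 0.2 = 0.004 SD to 0.10 × 0.5 = 0.05 SD.

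For scale, 80% retention of 900 gives 720, or 360 per arm. The standard error of the difference is √(2/360) = 0.0745 SD, so a bias of 0.025 SD is about one third of a standard error. With equal shares a constant gap cancels, but the outcome is still mixed.

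**Possible loss if proxy answers were set to missing.** This is the opposite practice, so it must not be added to the bias. The detectable difference at 80% power and two-sided 0.05 is (1.960 + 0.842) × √(2/n per arm). It is computed on observed self-reports only, with the share lost assumed:

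| Share without self-report | N | Detectable difference (SD) | Power at 0.3 SD |
|---|---|---|---|
| 0% | 720 | 0.209 | 0.981 |
| 5% | 684 | 0.214 | 0.975 |
| 10% | 648 | 0.220 | 0.968 |
| 20% | 576 | 0.233 | 0.950 |
| 30% | 504 | 0.250 | 0.920 |

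The 0.3 SD column uses the smallest effect size in the January 2019 power analysis, which was set for PART-O-17.

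**The case against.** The case against has real weight.

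- **The proxy footnote is narrow.** A reader might infer that proxies are barred from the QoLIBRI throughout. The text covers one enrolment scenario, and patients enrolled through a representative are re-assessed for capacity after discharge. Some of them may report for themselves by 6 months.
- **The significant-other mailout is a last step.** A reader might infer that it goes out for any hard-to-reach patient. The Mailout Option section first sends the patient's own form and continues the calls.
- **Proxy scoring is not directed.** The mailout paragraph does not say that the significant other answers in the patient's place, or that such answers count. The definitions elsewhere point the other way.
- **Respondent type may be captured.** The case report forms and the Manual of Procedures are not part of these documents and could hold such a field. The Participant Retention section already records reasons for missing follow-up, including an unavailable proxy.

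All four points stand, and they limit the claim. They do not remove it: the one instruction governing the mailout has no exclusion, and the definitions alone do not tell site staff what to put in the envelope.

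A further tempting inference is that QoLIBRI blanks under the proxy rule will be imputed, so that the outcome ceases to be self-report. The documents do not support this. Imputation depends on the missing-data mechanism and is reported beside complete-case results, and imputing a blank does not turn any observed score into a proxy rating. What remains is a separate, smaller gap. Values withheld because the patient could not self-report are doubtful candidates for missing at random, and the plan names no analysis for them.

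**Conclusion.** The concern holds in a limited form. The proxy rule and the significant-other mailout are not reconciled, so self-report of the QoLIBRI is not assured. The documents fail to rule out proxy ratings; they do not instruct that any be scored.

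The size cannot be known from the documents. On the assumed figures the bias is about 0.015 to 0.025 SD, and 0.05 SD at the edge of the wider range. The cost in power of excluding proxy answers is modest at 0.3 SD. These figures rest on an assumed difference in proxy share, a constant rater gap, and 720 patients followed. The matter is worth correcting because it touches the definition of a primary outcome and is cheap to settle, not because it threatens the trial's power.

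A reader might conclude that QoLIBRI should never be imputed for patients assessed only through a proxy. That goes too far. Dropping them would conflict with the plan's commitment to include all randomized cases, and it could itself introduce selection if proxy use differs by arm.

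**What to change.** 1. In Questionnaire Scheduling and Timing, state that the mailout to a significant other omits the QoLIBRI, and that any QoLIBRI completed by a proxy is treated as missing.
2. Record respondent type (patient, patient with help, proxy) for every patient questionnaire and report it by arm and visit.
3. In the Data Analysis Plan, keep all randomized patients in the intent-to-treat analysis. Report by arm how many QoLIBRI values were withheld under the proxy rule. Beside the planned imputation and complete-case analyses, add a missing-not-at-random sensitivity analysis for those values, for example imputed scores shifted by a range fixed in advance and allowed to differ by arm.

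Version 15.0 is dated 01-23-23, after the 10/31/2022 milestone for completing 12-month follow-up, while analyses are due 7/15/2023. For forms already returned, respondent type would have to be recovered from the mailout records where possible, and the analysis wording then matters most.

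The cost is a sentence in the procedure, a field or a record check, a short addition to the analysis plan, slightly fewer observed QoLIBRI values, and a little more analysis work.
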